7.1.6.2 Follow-up Visits

Subjects who discontinue trial treatment for a reason other than disease progression will move into the Follow-up Phase and should be assessed per institutional guidelines by radiologic imaging to monitor disease status. Every effort should be made to collect information regarding disease status until the start of new anti-neoplastic therapy, disease progression, death, end of the study or if the subject begins retreatment with pembrolizumab as detailed in Section 7.1.6.4. Information regarding post-study anti-neoplastic treatment will be collected if new treatment is initiated.

Subjects who are eligible to receive retreatment with pembrolizumab according to the criteria in Section 7.1.6.4 will move from the Follow-Up Phase to the Retreatment Period when they experience disease progression.

7.1.6.3 Survival Follow-up

Once a subject experiences confirmed disease progression or starts a new anti-cancer therapy, the subject moves into the survival follow-up phase and will be monitored every 6 months (\pm 30 days) to assess for survival status until death, withdrawal of consent, or the end of the study, whichever occurs first.

7.1.6.4 Retreatment Phase

Subjects who stop pembrolizumab with SD or better may be eligible for up to one year of additional pembrolizumab therapy if they progress after stopping study treatment. This retreatment phase is only available if the study remains open and the subject meets the following conditions:

Either

- Stopped initial treatment with pembrolizumab after attaining an investigator-determined confirmed CR according to RECIST 1.1 (Section 14.3), and
 - Was treated for at least 24 weeks with pembrolizumab before discontinuing therapy
 - Received at least two treatments with pembrolizumab beyond the date when the initial CR was declared

OR

- Had SD, PR or CR and stopped pembrolizumab treatment after 24 months of study therapy for reasons other than disease progression or intolerance

AND

- Experienced an investigator-determined confirmed radiographic disease progression after stopping their initial treatment with pembrolizumab
- Did not receive any anti-cancer treatment since the last dose of pembrolizumab
- Has a performance status of 0 or 1 on the ECOG Performance Scale
- Demonstrates adequate organ function as detailed in Section 5.1.2
- Female subject of childbearing potential should have a negative serum or urine pregnancy test within 72 hours prior to receiving retreatment with study medication.
- Female subject of childbearing potential should be willing to use 2 methods of birth control or be surgically sterile, or abstain from heterosexual activity for the course of the study through 120 days after the last dose of study medication (reference Section 5.5.2). Subjects of child bearing potential are those who have not been surgically sterilized or have been free from menses for $>$ 1 year.
- Male subject should agree to use an adequate method of contraception starting with the first dose of study therapy through 120 days after the last dose of study therapy.
- Does not have a history or current evidence of any condition, therapy, or laboratory abnormality that might interfere with the subject's participation for the full duration of the trial or is not in the best interest of the subject to participate, in the opinion of the treating investigator.

Subjects who restart treatment will be retreated at the same dose and dose interval as when they last received pembrolizumab. Treatment will be administered for up to one additional year. Subjects should be re-consented prior to start of re-treatment.

Visit requirements are outlined in Section 6.0 – Schedule of Assessments.

7.2 Assessing and Recording of Adverse Events

7.2.1 Definitions of Adverse Events

7.2.1.1 Adverse Event (AE)

An adverse event is defined as untoward medical occurrence associated with the use of a drug in humans, whether or not considered drug related. An adverse event can be ANY unfavorable and unintended sign (e.g. an abnormal laboratory finding), symptom, or disease temporarily associated with the use of a medicinal (investigational) product, whether or not considered related to the medicinal (investigational) product (attribution of ‘unrelated’, ‘unlikely’, ‘possible’, ‘probable’, or ‘definite’). Adverse events will be graded according to the NCI Common Toxicity Criteria, Version 4.0.

7.2.1.2 Serious Adverse Event (SAE)

A serious adverse event is any untoward medical occurrence resulting in one or more of the following:

- Results in death or ANY death occurring within 90 days of last dose of study drug (even if it is not felt to be drug related)
- Is life-threatening (defined as an event in which the patient was at risk of death at the time of the event; it does not refer to an event which hypothetically might have caused death if it were more severe)
- Requires inpatient hospitalization or prolongation of existing hospitalization

NOTE: Hospitalizations that are not considered SAEs are:

- Hospitalization planned prior to first administration of study drug
- Hospitalization for elective treatment of a pre-existing condition unrelated to the study medication
- Results in persistent or significant disability/incapacity
- Is a congenital anomaly or birth defect
- Is an important medical event (defined as a medical event(s) that may not be immediately life-threatening or result in death or hospitalization but, based upon appropriate medical and scientific judgment, may jeopardize the patient or may require intervention (e.g., medical, surgical) to prevent one of the other serious outcomes listed in the definition above). Examples of such events include, but are not limited to, intensive treatment in an emergency room or at home for allergic bronchospasm; blood dyscrasias or convulsions not resulting in hospitalization; or the development of drug dependency or drug abuse.
- Pregnancy

- Pregnancy of a patient or of the female partner of a male patient during the study or within 120 days after the last dose of study drug should be reported via an SAE report. Should pregnancy occur in a female participant during the treatment period, study drug should be discontinued and Merck notified immediately. Should a pregnancy occur in a female companion of a male participant during the treatment period, the male participant can continue treatment and Merck notified immediately. Any such pregnancy is to be followed until final outcome. Evaluating Adverse Events
- In addition to the above criteria, AEs meeting either of the below criteria, although not serious per ICH definition, are reportable to Merck in the same time frame as SAEs to meet certain local requirements. Therefore, these events are considered serious by Merck for collection purposes.
 - Is a new cancer (that is not a condition of the study)
 - Is associated with an overdose of pembrolizumab

An investigator who is a qualified physician will evaluate all adverse events according to the NCI Common Terminology for Adverse Events (CTCAE), version 4.0. Any adverse event which changes CTCAE grade over the course of a given episode will have each change of grade recorded on the adverse event case report forms/worksheets.

All adverse events regardless of CTCAE grade must also be evaluated for seriousness.

7.2.1.3 Unanticipated Problem

Unanticipated Problem (UP): any incident, experience, or outcome that meets all of the following criteria:

- 1) unexpected (in terms of nature, severity, or frequency) given (a) the research procedures are described in the protocol-related documents, such as the IRB-approved research protocol and informed consent document; and (b) the characteristics of the subject population being study;
- 2) related or possibly related to participation in the research; and
- 3) suggests that the research places subjects or others at a greater risk of harm (including physical, psychological, economic, or social harm) related to the research than was previously known or recognized.

Only a small subset of adverse events occurring in human subjects participating in research will meet these three criteria for an unanticipated problem. Furthermore, there are other types of incidents, experiences, and outcomes that occur during the conduct of human subjects research that represent unanticipated problems but are not considered adverse events. For example, some unanticipated problems involve social or economic harm instead of the physical or psychological harm associated with adverse events. In other cases, unanticipated problems place subjects or others at increased risk of harm, but no harm occurs.

7.2.1.4 Unexpected Adverse Event

An adverse event not mentioned in the Investigator's Brochure or package insert or the specificity or severity of which is not consistent with the Investigator's brochure or package insert.

Refer to Table 6 for additional details regarding each of the above criteria.

Table 6: Evaluating Adverse Events

An investigator who is a qualified physician, will evaluate all adverse events as to:

V4.0 CTCAE Grading	Grade 1	Mild; asymptomatic or mild symptoms; clinical or diagnostic observations only; intervention not indicated.
	Grade 2	Moderate; minimal, local or noninvasive intervention indicated; limiting age-appropriate instrumental ADL.
	Grade 3	Severe or medically significant but not immediately life-threatening; hospitalization or prolongation or hospitalization indicated; disabling; limiting self-care ADL.
	Grade 4	Life threatening consequences; urgent intervention indicated.
	Grade 5	Death related to AE
Seriousness	A serious adverse event is any adverse event occurring at any dose or during any use of pembrolizumab or vorinostat that:	
	†Results in death; or	
	†Is life threatening; or places the subject, in the view of the investigator, at immediate risk of death from the event as it occurred (Note: This does not include an adverse event that, had it occurred in a more severe form, might have caused death.); or	
	†Results in a persistent or significant disability/incapacity (substantial disruption of one's ability to conduct normal life functions); or	
	†Results in or prolongs an existing inpatient hospitalization (hospitalization is defined as an inpatient admission, regardless of length of stay, even if the hospitalization is a precautionary measure for continued observation. (Note: Hospitalization [including hospitalization for an elective procedure] for a preexisting condition which has not worsened does not constitute a serious adverse event.); or	
	†Is a congenital anomaly/birth defect (in offspring of subject taking the product regardless of time to diagnosis); or	
	Is a new cancer; (that is not a condition of the study) or	
	Is an overdose (whether accidental or intentional). Any adverse event associated with an overdose is considered a serious adverse event. An overdose that is not associated with an adverse event is considered a non-serious event of clinical interest and must be reported within 24 hours.	
	Other important medical events that may not result in death, not be life threatening, or not require hospitalization may be considered a serious adverse event when, based upon appropriate medical judgment, the event may jeopardize the subject and may require medical or surgical intervention to prevent one of the outcomes listed previously (designated above by a †).	
Duration	Record the start and stop dates of the adverse event. If less than 1 day, indicate the appropriate length of time and units	
Action taken	Did the adverse event cause pembrolizumab or vorinostat to be discontinued?	
Relationship to Pembrolizumab or Vorinostat	Did pembrolizumab or vorinostat cause the adverse event? The determination of the likelihood that pembrolizumab or vorinostat caused the adverse event will be provided by an investigator who is a qualified physician. The investigator's signed/dated initials on the source document or worksheet that supports the causality noted on the AE form, ensures that a medically qualified assessment of causality was done. This initialed document must be retained for the required regulatory time frame. The criteria below are intended as reference guidelines to assist the investigator in assessing the likelihood of a relationship between the test drug and the adverse event based upon the available information.	
	The following components are to be used to assess the relationship between pembrolizumab or vorinostat and the AE; the greater the correlation with the components and their respective elements (in number and/or intensity), the more likely pembrolizumab or vorinostat caused the adverse event (AE):	
	Exposure	Is there evidence that the subject was actually exposed to pembrolizumab or vorinostat such as: reliable history, acceptable compliance assessment (pill count, diary, etc.), expected pharmacologic effect, or measurement of drug/metabolite in bodily specimen?
	Time Course	Did the AE follow in a reasonable temporal sequence from administration of pembrolizumab or vorinostat? Is the time of onset of the AE compatible with a drug-induced effect?
	Likely Cause	Is the AE not reasonably explained by another etiology such as underlying disease, other drug(s)/vaccine(s), or other host or environmental factors

Relationship to Pembrolizumab or Vorinostat (continued)		The following components are to be used to assess the relationship between the test drug and the AE: (continued)
	Dechallenge	
Was pembrolizumab or vorinostat discontinued or dose/exposure/frequency reduced? If yes, did the AE resolve or improve? If yes, this is a positive dechallenge. If no, this is a negative dechallenge.
 
(Note: This criterion is not applicable if: (1) the AE resulted in death or permanent disability; (2) the AE resolved/improved despite continuation of pembrolizumab or vorinostat; or (3) the trial is a single-dose drug trial); or (4) pembrolizumab or vorinostat are only used one time.)

	Rechallenge	
Was the subject re-exposed to pembrolizumab or vorinostat in this study? If yes, did the AE recur or worsen? If yes, this is a positive rechallenge. If no, this is a negative rechallenge.
 
(Note: This criterion is not applicable if: (1) the initial AE resulted in death or permanent disability, or (2) the trial is a single-dose drug trial); or (3) pembrolizumab or vorinostat are used only one time).
 
NOTE: IF A RECHALLENGE IS PLANNED FOR AN ADVERSE EVENT WHICH WAS SERIOUS AND WHICH MAY HAVE BEEN CAUSED BY PEMBROLIZUMAB OR VORINOSTAT, OR IF REEXPOSURE TO PEMBROLIZUMAB OR VORINOSTAT POSES ADDITIONAL POTENTIAL SIGNIFICANT RISK TO THE SUBJECT, THEN THE RECHALLENGE MUST BE APPROVED IN ADVANCE BY THE SPONSOR AS PER DOSE MODIFICATION GUIDELINES IN THE PROTOCOL.

	Consistency with Trial Treatment Profile	Is the clinical/pathological presentation of the AE consistent with previous knowledge regarding the pembrolizumab or vorinostat or drug class pharmacology or toxicology?
The assessment of relationship will be reported on the case report forms /worksheets by an investigator who is a qualified physician according to his/her best clinical judgment, including consideration of the above elements.		
	Record one of the following	Use the following scale of criteria as guidance (not all criteria must be present to be indicative of pembrolizumab or vorinostat relationship).
Yes, there is a reasonable possibility of pembrolizumab or vorinostat relationship.	There is evidence of exposure to pembrolizumab or vorinostat. The temporal sequence of the AE onset relative to the administration of pembrolizumab or vorinostat is reasonable. The AE is more likely explained by pembrolizumab or vorinostat than by another cause.	
No, there is not a reasonable possibility pembrolizumab or vorinostat relationship	Subject did not receive pembrolizumab or vorinostat OR temporal sequence of the AE onset relative to administration of the pembrolizumab or vorinostat is not reasonable OR there is another obvious cause of the AE. (Also entered for a subject with overdose without an associated AE.)	

7.2.2 Definition of an Overdose

For purposes of this trial, an overdose of pembrolizumab will be defined as any dose of 1,000 mg or greater (≥ 5 times the indicated dose). No specific information is available on the treatment of overdose of pembrolizumab. Appropriate supportive treatment should be provided if clinically indicated. An overdose of vorinostat will be defined as any dose of ≥ 5 times the current dose being given (i.e. if 100 mg is indicated, 500 mg would be considered treatment overdose, and if 200 mg is indicated, 1000 mg would be considered treatment overdose). In the event of overdose, the subject should be observed closely for signs of toxicity. Appropriate supportive treatment should be provided if clinically indicated.

If an adverse event(s) is associated with (“results from”) the overdose of investigational product, the adverse event(s) is reported as a serious adverse event, even if no other seriousness criteria are met.

If a dose of investigational product meeting the protocol definition of overdose is taken without any associated clinical symptoms or abnormal laboratory results, the overdose is reported as a non-serious Event of Clinical Interest (ECI), using the terminology “accidental or intentional overdose without adverse effect.”

All reports of overdose with and without an adverse event must be reported as described in sections 7.2.5 and 10.5.

7.2.3 Pregnancy and Lactation

Although pregnancy and lactation are not considered adverse events, it is the responsibility of investigators or their designees to report any pregnancy or lactation in a subject (spontaneously reported to them), including the pregnancy of a male subject's female partner that occurs during the trial or within 120 days of completing the trial, or 30 days following cessation of treatment if the subject initiates new anticancer therapy, whichever is earlier. All subjects and female partners of male subjects who become pregnant must be followed to the completion/termination of the pregnancy. Pregnancy outcomes of spontaneous abortion, missed abortion, benign hydatidiform mole, blighted ovum, fetal death, intrauterine death, miscarriage and stillbirth must be reported as serious events (Important Medical Events). If the pregnancy continues to term, the outcome (health of infant) must also be reported.

Such events must be reported as within 24 hours to the Sponsor and within 2 working days to Merck Global Safety. (Attn: Worldwide Product Safety; [contact])

7.2.4 Events of Clinical Interest

Selected non-serious and serious adverse events are also known as Events of Clinical Interest (ECI) and must be recorded as such on the Adverse Event case report forms and reported as described in sections 5.2.1.6 and 10.5. Events of Clinical Interest for this trial include:

1. An overdose of pembrolizumab, as defined in Section 7.2.2 - Definition of an Overdose, that is not associated with clinical symptoms or abnormal laboratory results.

2. An elevated AST or ALT lab value that is greater than or equal to 3X the upper limit of normal and an elevated total bilirubin lab value that is greater than or equal to 2X the upper limit of normal and, at the same time, an alkaline phosphatase lab value that is less than 2X the upper limit of normal, as determined by way of protocol-specified laboratory testing or unscheduled laboratory testing.*

*Note: These criteria are based upon available regulatory guidance documents. The purpose of the criteria is to specify a threshold of abnormal hepatic tests that may require an additional evaluation for an underlying etiology. The trial site guidance for assessment and follow up of these criteria can be found in the Investigator Trial File Binder (or equivalent).

3. Additional adverse events:

A separate guidance document has been provided entitled “Event of Clinical Interest Guidance Document” (previously entitled, “Event of Clinical Interest and Immune-Related Adverse Event Guidance Document”). This document can be found in Appendix 14.5 and provides guidance regarding identification, evaluation and management of ECIs and irAEs.

ECIs (both non-serious and serious adverse events) identified in this guidance document from the date of first dose through 90 days following cessation of treatment, or 30 days after the initiation of a new anticancer therapy, whichever is earlier, need to be reported as described in sections 5.2.1.6 and 10.5 regardless of attribution to study treatment, consistent with standard SAE reporting guidelines.

Subjects should be assessed for possible ECIs prior to each dose. Lab results should be evaluated and subjects should be asked for signs and symptoms suggestive of an immune-related event. Subjects who develop an ECI thought to be immune-related should have additional testing to rule out other etiologic causes. If lab results or symptoms indicate a possible immune-related ECI, then additional testing should be performed to rule out other etiologic causes. If no other cause is found, then it is assumed to be immune-related.

7.3 Participating Site Reporting Responsibilities

7.3.1 Reporting SAEs, ECIs and Pregnancy to the Coordinating Center (IU Simon Comprehensive Cancer Center)

Any serious adverse event, unanticipated problem, event of clinical interest or pregnancy occurring from the first dose of vorinostat to within 90 days from the last dose of study drug must be reported to the IU Simon Comprehensive Cancer Center within 24 hours of notification or discovery of the incident, using the MedWatch Form 3500A (Mandatory Reporting). This form must be accompanied by a cover letter which: identifies the event, is signed by the local principal investigator or treating physician, includes the applicable study number and title, and contains the following:

- Site assessment of the event attribution to investigational treatment or study procedure
- Site assessment of event expectedness (expected vs. unexpected)

- Assessment of whether or not the research places subjects at a greater risk of harm than was previously known or recognized
- Assessment of the event's affect on the risk to benefit ratio
- Statement as to whether the informed consent statement should reflect changes in the potential risks involved
- Statement as to whether the event has been reported previously, and if so, whether the frequency is considered unusually high

Send to: IUSCC Clinical Trials Office
 ATTN: Multicenter coordinator/ IUSCC-0551
 Preferred E-mail: [contact]
 Backup [contact]

All SAEs must also be entered into OnCore for **monthly review** by the DSMC Coordinator. The Multicenter Network Administrator, or designee, will distribute all reports meeting expedited reporting criteria to all participating sites, the FDA and to Merck. Copies of all serious adverse event reports will be kept on file in the IU Simon Comprehensive Cancer Center Clinical Trials Office.

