6.0 SCHEDULE OF ASSESSMENTS

Trial Period:	Screening Phase	Run-in Phase ¹³	Combination Phase								End of Treatment	Post-Treatment			
			1	2	3	4	To be repeated beyond 8 cycles					Safety Follow-up ²	Follow-up Visits ³	Survival Follow-up	
Treatment Cycle	Screening ¹ (Visit 1)	-2	-1	1	D 14				5	6	7	8			
Scheduling Window (Days):	-28 days to start of first cycle	± 3	± 3	± 3	± 3	± 3	± 3	± 3	± 3	± 3	± 3	± 3	30 days post discon ± 3	Per institutional guidelines	Every 6 months ± 30
Administrative Procedures															
Informed Consent	x														
Inclusion/Exclusion Criteria	x														
Demographics and Medical History	x														
Registration	x														
Prior and Concomitant Medication Review	x														
Trial Treatment Administration		x	x	x	x	x	x	x	x	x	x	x			
Post-study anticancer therapy status												x	x	x	
Survival Status														x	
Clinical Procedures/Assessments															
Review Adverse Events			x	x		x	x	x	x	x	x	x	x		
Full Physical Examination ⁴	x	x	x	x		x	x	x	x	x	x	x			
Drug Compliance Review			x		x	x	x	x	x	x	x	x			
Vital Signs, Weight and Height (Screening Only)	x	x	x	x		x	x	x	x	x	x	x			
ECOG Performance Status	x	x	x	x		x	x	x	x	x	x	x			
Laboratory Procedures/Assessments⁹															

Trial Period:	Screening Phase	Run-in Phase ¹³	Combination Phase								End of Treatment	Post-Treatment			
			1	2	3	4	To be repeated beyond 8 cycles					Safety Follow-up ²	Follow-up Visits ³	Survival Follow-up	
Treatment Cycle	Screening ¹ (Visit 1)	-2	-1	1	D 14				5	6	7	8			
Scheduling Window (Days):	-28 days to start of first cycle	± 3	± 3	± 3	± 3	± 3	± 3	± 3	± 3	± 3	± 3	± 3	30 days post discon ± 3	Per institutional guidelines	Every 6 months ± 30
Pregnancy Test – Urine or Serum β-HCG	x ⁵						x ⁵								
PT/INR and aPTT	x														
CBC with Differential	x	x	x	x	x	x	x	x	x	x	x	x			
Comprehensive Serum Chemistry Panel	x	x	x	x		x	x	x	x	x	x	x			
Urinalysis	x		x		x		x		x		x	x			
T3, FT4 and TSH	x		x		x		x		x		x	x			
HgbA1c ¹¹	x	x	x	x	x	x	x	x	x	x	x				
Prostate Specific Antigen Test			x		x		x		x		x	x			
Efficacy Measurements															
Tumor Imaging – CT ¹⁶	x						x ¹³			x ¹⁶			x ¹²		
Tumor Imaging - Bone Scan	x						x ^{12, 13}			x ^{12,16}			x ¹²		
Tumor Imaging - ⁶⁸ Ga-PSMA-11 PET Scan ¹⁷	x						x ¹⁷								
Tumor Biopsies/Archival Tissue Collection/Correlative Studies Blood															
Archival (when available), Newly Obtained Tissue Collection (optional) ⁷	x			x ¹⁵											

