7.1.2.2 Full Physical Exam

The investigator or qualified designee will perform a complete physical exam during the screening period. Clinically significant abnormal findings should be recorded as medical history. Full physical exams may also be done by the investigator or qualified designee throughout participation in the trial as clinically indicated and as specified in the Schedule of Assessments (section 6.0.) After the first dose of study intervention, new clinically significant abnormal findings should be recorded as AEs.

Investigators should pay special attention to clinical signs related to previous serious illnesses.

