7.1.2.5 Tumor Imaging and Assessment of Disease

Imaging studies (CT and bone scan) will be performed at baseline, before Cycle 3, every 3 cycles thereafter and at treatment discontinuation as described in Section 7.1.4.1 below. CT modalities should be done according to standard of care for the patient's disease. Bone scans should be done at baseline and then only as clinically indicated.

Patients in Cohort C (prostate) will have two PET scans using ⁶⁸Ga-PSMA-11: once at baseline and then at 12 weeks (Cycle 4) Not all patients in Cohort C will have the additional PET scans. This determination will be made by the Principal Investigator.

Participant eligibility will be determined using local assessment (Investigator assessment) based on RECIST 1.1. In addition, images (including via other modalities) that are obtained at an unscheduled time point to determine disease progression, as well as imaging obtained for other reasons, but which demonstrate radiologic progression, should also be used to determine progression.

When the Investigator identifies radiographic progression per RECIST 1.1, efforts should be made to verify radiologic PD. Treatment should continue until PD has been verified. Regardless of whether PD is verified, if the Investigator considers the participant has progressed, but elects to implement irRC, the Investigator will assess for confirmation of progression by irRC at subsequent time points.

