7.1.2.6 Tumor Tissue Collection and Correlative Studies Blood Sampling

7.1.2.6.1 Pharmacodynamic Analysis

All biopsies on this trial are optional for patients. Whenever possible, archival tissue from a tumor lesion will be obtained at screening. If archived tissue is not available, patients will be given the option to consent to a biopsy during the screening phase. Patients will also be given the option to consent to a biopsy on Day 14 of Cycle 1 (window -3 days). The treatment biopsy should occur approximately 2 hours following the most recent dose of vorinostat on cycle 1 day 14. To ensure that these samples are obtained at the correct time, patients are urged to take their vorinostat dose in the clinic on the day of on-treatment sample collection.

Biopsy for tumor tissue collection will only be done on patients who have accessible tumor per institutional guidelines. Missed tissue collection will not be considered a protocol deviation for the purposes of this study, as tissue collection is an exploratory objective for this study.

Biomarker studies on tumor and blood biospecimens will be carried out to help understand the mechanism of action of the pembrolizumab and vorinostat combination. The run-in phase will help to assess the effect of single agents on the potential biomarkers. Results from these correlative studies will help in the identification of potential biomarkers of response to the pembrolizumab plus vorinostat combination, ultimately leading to the development of a patient selection strategy for further clinical investigation. As such, collection of tumor and blood biospecimens at baseline and on study will be of great importance.

The pharmacodynamics of vorinostat and pembrolizumab will be evaluated. Correlative studies will include assessment of immune effects Tregs, MDSCs and other immune cells at defined time points per the study calendar (i.e., baseline, Run-in Phase Cycle -2 Days 1 and 14 [Dose Expansion Phase only], Cycle 1 Day 1 before dosing, Cycle 2 Day 1 before dosing, every other cycle day 1 before dosing thereafter, and at treatment discontinuation).

Imaging studies (CT and bone scan) will be performed at baseline, before Cycle 3, every 3 cycles thereafter and at treatment discontinuation.

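### The 24-hour site reporting window in Section 7.3.1 opens at the first vorinostat dose, so it leaves out serious complications of the optional screening biopsy

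*Combined protocol and SAP*

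**What the plan says.** Section 7.3.1 sets the participating sites' 24-hour duty to the coordinating center. It covers SAEs, unanticipated problems, events of clinical interest and pregnancies "occurring from the first dose of vorinostat to within 90 days from the last dose" of study drug. The cover letter that goes with each report must contain, among other items, "Site assessment of the event attribution to investigational treatment or study procedure".

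The Schedule of Assessments (Section 6.0) allows screening from minus "28 days to start of first cycle". Section 7.1.2.6.1 places a research procedure in that period: "If archived tissue is not available, patients will be given the option to consent to a biopsy during the screening phase". The same section makes all biopsies optional, limits them to patients with accessible tumor, and offers a second biopsy on Day 14 of Cycle 1. Section 7.1.2.5 adds a baseline PSMA PET scan for some Cohort C patients, selected by the Principal Investigator.

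On recording, Section 7.1.2.2 sends abnormal findings from the screening examination to medical history, and then says: "After the first dose of study intervention, new clinically significant abnormal findings should be recorded as AEs".

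**The concern.** The report form asks about harm from study procedures, but the reporting window starts after the first invasive procedure that the study offers. A patient admitted to hospital with a complication of a screening biopsy has been harmed by taking part in the research, and Section 7.3.1 does not oblige the site to tell the coordinating center.

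Two things are at stake. First, the coordinating center passes expedited reports on to the other sites, the FDA and the drug supplier, and it oversees a protocol that offers a further biopsy two weeks into combination treatment. Experience with the screening biopsy bears directly on the risk of that second one. Second, the safety population (Section 8.3.2) requires at least one dose of study medication. If the complication stops a patient from being dosed, the event also appears in none of the safety tables of Section 8.10. Prompt reporting is then the main way it could be seen.

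**Working it through.** No statistical calculation applies, and the plan gives no figure to reproduce. The check sets the start of each reporting rule beside the time at which the procedure can happen.

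**Timing.** Take the first day of the first cycle as day 0. Screening runs from day −28 to day 0, and the biopsy can fall anywhere in it. The 7.3.1 window opens at the first vorinostat dose, so no earlier than day 0. The uncovered interval is therefore up to 0 − (−28) = 28 days.

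**Routes and definitions side by side.**

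| Section | What it governs | Start | A pre-dose biopsy complication? |
|---|---|---|---|
| 7.3.1, first sentence | Site to coordinating center, 24 hours | First vorinostat dose | Not covered |
| 7.3.1, closing paragraph; 7.4.5 | Entry of all SAEs in OnCore for the safety committee | None stated | Covered only if it counts as an SAE |
| 9.7 | OnCore capture of all SAEs in 1 business day, with procedures among the attributions | None stated | Covered only if it counts as an SAE |
| Site IRB paragraph at the end of 7.3 | SAEs and unanticipated problems to the site's own IRB | None stated; local rules apply | Depends on local rules; goes to the IRB, not the coordinating center |
| 7.4.1 | Unanticipated problems to the coordinating center's IRB, 5 business days | None stated | Prompt report only if unexpected, related and indicating greater risk |

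**Does it count as an SAE?** The definitions differ.

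- Section 7.2.1.1 ties an adverse event to use of a drug.
- Table 6 defines an SAE as an adverse event at any dose, or during any use, of pembrolizumab or vorinostat. On that reading an event in an undosed patient is not an SAE.
- Section 7.2.1.2 counts any untoward occurrence that leads to inpatient hospitalization, with no dosing condition on that item. On that reading the event is an SAE.

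The undated OnCore routes therefore catch the event under one definition and miss it under the other two.

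**Would anyone be prompted to look?** As the schedule table reads in the extracted text, the adverse-event review row has no mark at Screening or at run-in Cycle −2. The first marks are at Cycle −1 for patients who have the run-in, and at Cycle 1 for those who do not. For the second group, Section 5.2.1.6 (timing of dose administration) puts that visit's assessments ahead of treatment, so a question on the dosing day itself could bring the event to light. No review is marked before that day, and Section 7.1.2.2 starts recording new findings as adverse events only after the first dose.

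**The case against.** The strongest reply is that 7.3.1 is one route among several. OnCore entry of all SAEs is required in three places without a start date. Section 9.7 names procedures as a possible cause. OnCore is the coordinating center's own database. The definition of an unanticipated problem (Section 7.2.1.3) turns on participation in the research and not on dosing. All of this stands. A reader might infer from 7.3.1 that no reporting of any kind begins before the first dose, or that a biopsy-related admission would reach neither the coordinating center nor the safety committee. The documents do not support that. They leave the matter unclear, because the undated SAE routes depend on definitions that disagree.

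The unanticipated-problem route helps only in part. A recognized biopsy complication may fail the test of being unexpected, although the test also covers severity and frequency, so an unusually severe or frequent complication could pass it.

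A reader might also give the baseline PSMA PET equal weight. That is not supported either. Section 5.1.1 restricts prostate enrollment to the coordinating center and its affiliates. Patients at the coordinating center fall under Section 7.4, which has no first-dose limit, and the documents do not say whether affiliates count as participating sites. The scan is also limited to a subset of one cohort.

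Finally, it is tempting to put a number on the missed events. The documents give neither a count of screening biopsies nor a complication rate, so any such number would be assumption alone.

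**Conclusion.** The point holds in a narrow form, and its severity is minor. The 24-hour rule in 7.3.1, as worded, excludes a serious complication of the optional screening biopsy for up to 28 days before the first cycle, while the same section asks whether a study procedure was the cause. The other routes may cover such an event, but the protocol does not settle whether they do, because Sections 7.2.1.1 and 7.2.1.2 and Table 6 do not agree on whether drug exposure is needed.

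The conclusion rests on reading 7.3.1 literally and on the schedule row as extracted. The expected frequency cannot be derived from the documents. It is limited by the biopsy being optional, offered at screening only when archival tissue is unavailable, and confined to accessible tumors. No efficacy estimate, sample size or stopping boundary is affected.

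**What to change.** 1. In Section 7.3.1, start the 24-hour report at signed consent for SAEs and unanticipated problems related to a procedure done for the study. This means chiefly the optional screening biopsy, and the baseline PSMA PET where a participating site performs it. Leave the start for all other events as it is.
2. Align the definitions in Sections 7.2.1.1 and 7.2.1.2 and Table 6 with this, so that a serious procedure-related event before dosing is plainly an SAE and the OnCore and safety committee rules apply to it.
3. In the Schedule of Assessments, add an adverse-event check before the first dose for patients who had such a procedure, and make the recording rule in Section 7.1.2.2 consistent with it.

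The cost is protocol wording, one short check in the patients concerned, and a few extra reports. Treatment, endpoints and sample size are unchanged.
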